## 7. PLANNED ANALYSIS

### *General Remarks*

The format of the listings and tables will follow the BI guideline "Reporting of clinical trials and project summaries" (001-MCG-159) ([7](#)).

The individual values of all patients will be listed, including those collected during the off-treatment period. Listings will generally be sorted by country, centre number, patient number and visit (if visit is applicable in the respective listing). (see [Section 7.8.1](#) below for details).

The following standard descriptive statistical parameters will be displayed in summary tables of continuous variables:

N	number of non-missing observations
Mean	arithmetic mean
SD	standard deviation
Min	minimum
Q1	lower quartile
Median	median
Q3	upper quartile
Max	maximum

Statistical parameters will be displayed to a defined number of decimal places as specified in the BI guideline "Reporting of clinical trials and project summaries" ([7](#)).

Tabulations of frequencies for categorical data will include all possible categories and will display the number of observations in a category as well as the percentage (%) relative to the respective patient set (unless otherwise specified, all patients in the patient set irrespective of whether they have non-missing values or not). Percentages will be rounded to one decimal place. The category missing will be displayed only if there are actually missing values.

Disposition of the patient population for each trial part (re-induction or overall maintenance) will be summarised by presentation of the frequency of patients enrolled, treated, enrolled but not treated, who completed all doses of trial medication as planned, who completed the PE visit (EOT), who completed the trial (EOS), and who were prematurely discontinued, by reason. Additional summaries by the parent trial will be produced, and, summaries of the maintenance period disposition according to whether or not a patient experienced re-induction treatment or not will also be done. The frequency of patients with iPDs will also be presented; the iPDs will be listed per patient.

To better illustrate the long-term efficacy of the overall maintenance treatment (defined in [Table 6.1: 4](#)), a summary table regarding patient status over time will be added. The cumulative frequency of patients for the following categories will be displayed based on 12-week interval:

- ongoing on study medication, i.e., without early treatment discontinuation by the time point

- Occurrence of a disease flare, or intake of disease flare medication
- Intake of rescue medication
- Any of the above
- pre-maturely stopped study medication, i.e., discontinued study medication by the time point
  - Occurrence of a disease flare, or intake of a disease flare medication
  - Intake of rescue medication
  - Death
  - Any of the above

For details on the requirements of the first interim data snapshot of this trial, refer to additional [Section 9.2.1](#). The second interim analysis requirements are specified in [Section 9.2.2](#).

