3. DESCRIPTION OF DESIGN AND TRIAL POPULATION

3.1 OVERALL TRIAL DESIGN AND PLAN

This open label (OL), 7 year, single group, long-term extension study investigates the long term safety and efficacy of BI 655130 (SPESOLIMAB) in patients with moderate-to-severe ulcerative colitis who have completed treatment in previous BI 655130 (SPESOLIMAB) induction trials 1368-0005 Part I and 1368-0004.

Approximately 160 patients who meet the entry criteria are planned to be included in the trial from previous induction trials 1368-0005 Part I and 1368-0004. The treatment will be open-label. Trial will consist of a screening period lasting up to 7 days, followed by a 336 weeks maintenance treatment period and a 16 weeks safety follow-up period. Patients rolling-over into 1368-0017 trial must complete the 12 weeks treatment period (until EOT visit) in the previous induction trial. Patients will be treated according to their previous trial outcome in a following way:

- Patients who have completed treatment in the previous trials showing a clinical response at week 12 will receive BI 655130 (SPESOLIMAB) s.c. maintenance treatment (300mg q4w s.c.) through week 336 of this extension study ([Flowchart 1](#)).
- Patients who have completed treatment in the previous trials, but did not achieve a clinical response at week 12, will receive BI 655130 (SPESOLIMAB) i.v. re-induction treatment (1200mg q4w i.v. for 12 weeks). Those patients who subsequently reach the clinical response (versus baseline of original induction trial) at week 12 of re-induction period, will be entered into the 336 weeks s.c. maintenance treatment phase ([Flowchart 2](#)); while non-responders will be discontinued from treatment and complete early EOT visit and safety follow-up period.
- Patients ongoing on maintenance treatment when CTP version 05 is approved will be asked to re-consent to the change in treatment frequency. After consent, patients will switch from q12w regimen to q4w regimen. Patients who do not wish to consent to this change will be discontinued from the study.

A schematic overview of trial design is shown in [Figures 3.1:1](#) and [3.1:2](#).

Proprietary confidential information © 2022 Boehringer Ingelheim International GmbH or one or more of its affiliated companies

[figure not shown]
Figure 3.1:1 Trial design for responders and non-responders

RESPONDERS

Figure 3.1:2 Trial design in case of a disease flare

DISEASE FLARE

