### **3. INTRODUCTION**

As per International Conference on Harmonisation (ICH) E9 ([1](#)), the purpose of this document is to provide a more technical and detailed elaboration of the principal features of the analysis described in the CTP and its amendments, and to include detailed procedures for executing the statistical analysis of the primary and secondary variables and other data.

This trial statistical analysis plan (TSAP) assumes familiarity with the clinical trial protocol (CTP). In particular, the TSAP is based on the planned analysis specification as written in CTP Section 7 “Statistical Methods and Determination of Sample Size”. Therefore, TSAP readers may consult the CTP for more background information on the study, e.g., on study objectives, study design and population, treatments, definition of measurements and variables, planning of sample size.

For other biomarkers not specified as endpoints, a separate document will complement this TSAP.

The statistical analyses will be performed within the validated working environment CARE, including SASTM (current Version 9.4, by [REDACTED]), and a number of SASTM-based tools (e.g., macros for the analyses of AE data or laboratory data; Report Appendix Generator system (RAGe) for compilation/formatting of the CTR appendices).

Since the primary aim of this study is to collect long-term safety and efficacy data on the use of spesolimab (BI 655130) in this population, multiple interim analyses will be done over the 7-year conduct phase of this trial in order to support, for example, regulatory interactions, Clinical Trial Authorizations (CTA), and MAA/BLA submissions, but also to provide important safety and efficacy information to the sponsor to guide further development of the compound, and to the investigators via IB updates and publications. Any data cut-off to be used for the reporting of trial data at interim will be presented in either a separate data cleaning plan, or in an appendix to this TSAP. If considered appropriate, an access plan may be developed at the time of the interim which describes those personnel who will be allowed access to the results of the interim data analysis.

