#### Efficacy imputation rules

The following rules apply for all treatment periods with defined efficacy endpoints. Missing data imputation, when performed, will not be done for missing assessments due to implementation of any cut-off date.

The following imputation strategy will be applied to the reporting of continuous efficacy data.

- Observed cases (OC) approach: prior to observing the applicable efficacy endpoint, data will be reported with no imputation performed on the missing data irrespective of whether the data is considered to be randomly missing, or missing due to prior occurrence of an applicable intercurrent event.

The following imputation strategy will be important for the display of binary efficacy data:

- No Response Imputation [NRI]: prior to observing the applicable binary efficacy endpoint, all missing data will be set to non-response irrespective of whether the data is considered to be randomly missing, or missing due to prior occurrence of an applicable intercurrent event. Only patients continuing at this visit per time window before interim cut-off will be included in the denominator.

The following imputation strategy will be important for the display of, i.e. safety laboratory data:

- Observed cases including values after any use of rescue medication (OC-IR): this approach is an extension of the OC approach which includes all values which were measured both before and after any rescue medication intake. The analysis using the OC-IR approach is then only based on the patients with observed data.

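### As written in SAP Section 7, the interim patient-status table counts patients who have not yet reached a given week as still on treatment, so it overstates retention at later weeks

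*SAP*

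**What the plan says.** The general remarks of SAP Section 7 introduce a status table for the overall maintenance period, meant to illustrate long-term efficacy. Its layout is stated as follows: "The cumulative frequency of patients for the following categories will be displayed based on 12-week interval".

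There are two main categories. The first is "ongoing on study medication, i.e., without early treatment discontinuation by the time point". The second is "pre-maturely stopped study medication, i.e., discontinued study medication by the time point". Each is followed by rows for flare or flare medication, rescue medication and any of these; the second also has a row for death. No category covers patients who have not yet reached the time point.

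The same general remarks fix the base for percentages: "unless otherwise specified, all patients in the patient set irrespective of whether they have non-missing values or not". Nothing different is specified for this table.

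SAP Section 3 announces that "multiple interim analyses will be done over the 7-year conduct phase of this trial", to serve regulatory interactions and submissions, investigator brochure updates and publications. Protocol Section 3.1 describes screening "followed by a 336 weeks maintenance treatment period".

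Elsewhere the SAP does deal with cut-offs. For binary efficacy data under non-response imputation, Section 6.6.2 says: "Only patients continuing at this visit per time window before interim cut-off will be included in the denominator". Section 7.8.1 censors time at risk for adverse events at the cut-off date of an interim analysis.

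**The concern.** Patients entered maintenance at different dates, so at any interim their possible follow-up differs. For someone whose week 96 lies after the cut-off, status at week 96 is unknown. The written definition nevertheless gives that person a status: no discontinuation has been recorded by week 96, so the person is ongoing. Follow-up cut short by the calendar is read as successful retention.

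The effect grows with the week, because more patients have not reached the later weeks, and those are the weeks for which a long-term table is read. This is a single-arm trial without a comparator column, so nothing else in the table would reveal the distortion. The readers are those of the interim reports.

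**Working it through.** The documents give no retention figure, so there is no planned number to reproduce. The check has three parts.

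**1. What the rule does to one patient.** Take 25 weeks of maintenance at the cut-off, with drug not stopped.
- Week 24: observed, ongoing. Correct.
- Week 48: not observed. The definition asks only whether a discontinuation has occurred by week 48. None has, so ongoing.
- Week 96 and every later column: the same.

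The two main categories are complements, so every patient in the maintenance safety set (SAF-MT) falls into one of them, and all are in the denominator.

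**2. Whether such patients must exist at interims.** The original protocol date is 20 March 2018 (Protocol synopsis), and no patient can have started before it.
- To the reported interim cut-off of 19 February 2020 (Protocol Section 1.4): 701 days / 7 = 100.1 weeks.
- To the date of SAP version 4.0, 13 January 2021 (SAP Section 10): 1030 / 7 = 147.1 weeks.

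At those dates nobody could have passed about week 100 or week 147 of a 336-week period. Trial 1368-0005 had its last patient visit on 18 May 2020 (Protocol Section 1.4), which is 240 / 7 = 34 weeks before 13 January 2021.

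**3. How large the effect could be.** Everything in this part is assumed and none of it is in the documents. Let follow-up available at the cut-off, f, be uniform between a = 21 and b = 119 weeks. This corresponds to entry from about October 2018 to 17 August 2020 (18 May 2020 plus 13 weeks) and a cut-off on 13 January 2021. Let time to discontinuation be exponential with median m, so S(t) = 2^(−t/m) and λ = ln 2 / m.

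Share ongoing at week w under the written rule, the mean of S(min(f, w)):

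P(w) = { [S(a) − S(w)] / λ + (b − w)·S(w) } / (b − a)

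For m = 48: λ = 0.01444 and S(21) = 0.7384.
- Week 48: (0.7384 − 0.5000)/0.01444 = 16.51; (119 − 48) × 0.5 = 35.50; sum 52.01 / 98 = 53.1%. True value 50%. Excess 3 points.
- Week 96: (0.7384 − 0.2500)/0.01444 = 33.82; (119 − 96) × 0.25 = 5.75; sum 39.57 / 98 = 40.4%. True value 25%. Excess 15 points.

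The share that could not have reached week w is (w − 21)/98: 28% at week 48 and 77% at week 96.

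Other assumptions, for range:

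| Follow-up at cut-off | Retention assumption | Week 48: written / true | Week 96: written / true |
|---|---|---|---|
| 21–119 weeks | median 24 weeks | 28.5% / 25% | 18.5% / 6.3% |
| 21–119 weeks | median 48 weeks | 53.1% / 50% | 40.4% / 25% |
| 21–119 weeks | median 96 weeks | 72.7% / 70.7% | 62.5% / 50% |
| 0–100 weeks | 30% at week 48 | 43.5% / 30% | 36.6% / 9% |
| 0–100 weeks | 50% at week 48 | 60.6% / 50% | 52.9% / 25% |
| 0–100 weeks | 70% at week 48 | 76.8% / 70% | 70.6% / 49% |
| 0–147 weeks | 50% at week 48 | 57.2% / 50% | 44.0% / 25% |

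Beyond the longest follow-up the written rule goes flat. In the 0–100 week case with 50% retention at week 48, it would show 52.9% in any column up to week 336 that is printed, although no patient has been observed there.

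**The case against.** The strongest objection is that the error arises only at interims, and interim rules are the text that cannot be seen. Section 7 sends the requirements of the first and second interims to Sections 9.2.1 and 9.2.2, which were removed from the text reviewed. Those sections may limit the table or its denominator, so they cannot be treated as missing from the plan. This stands, and the point is confined to Section 7 as written. It does not dispose of the point, because those sections are tied to two interims and Section 3 plans multiple. Section 3 also says that each cut-off will be presented in a data cleaning plan or an appendix, but that fixes the cut-off, not how this table treats it.

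Second, Section 6.6.2 rules out imputation for assessments missing because of a cut-off, and Section 7 allows a missing category. On that reading, patients short of a week might be set aside. But the imputation rule concerns efficacy assessments, and the definition of ongoing assigns everyone a status, so nothing is left to be missing. A careful programmer might still drop these patients or the unreached columns; the SAP does not ask for it, and its default base points the other way.

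Third, the effect is temporary at any given week. That stands. Recruitment is closed (Protocol Section 1.4). On the assumed latest entry of 17 August 2020, everyone could have reached week 48 by July 2021 and week 96 by June 2022. At later interims the distortion moves to later weeks.

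A reader might also infer that this table is the main long-term efficacy display. The documents do not support that: clinical remission at week 336 is the secondary endpoint, and SAP Table 6.3: 1 provides for further endpoints in the overall maintenance period, whose definitions were not available for this review.

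**Conclusion.** The point holds for SAP Section 7 as written, for any analysis with a data cut-off, unless Sections 9.2.1 and 9.2.2 already restrict the table for the first two interims. The direction is certain whenever some patients have not reached the week and some of them would still stop, flare or need rescue: retention too high; discontinuation, and flare and rescue summed over both main categories, too low. The flare and rescue rows within the ongoing category alone could move either way.

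The size is not derivable from the documents. About 3 points at week 48 and 15 points at week 96 is an illustration. It rests on uniform follow-up of 21 to 119 weeks, a constant discontinuation hazard with a 48-week median, and a SAP version date used as the cut-off. The other scenarios shown run from 2 to 14 points at week 48 and from 12 to 28 points at week 96.

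A reader might infer that the trial's reported long-term results are biased. They are not bound to be. The table is descriptive and is neither the primary nor the secondary endpoint, the SAP does not say which interims will carry it, and at the final analysis every patient will have completed or discontinued.

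**What to change.** Add to SAP Section 7 that, for any analysis with a data cut-off, each 12-week column includes in numerator and denominator only patients whose planned date for that week falls on or before the cut-off. Patients who discontinued earlier stay in if their planned date meets this condition. Show the number of such patients in each column, and do not extend columns beyond observed follow-up. If Section 9.2.1 or 9.2.2 already says this, move the rule to Section 7 so that it covers every interim.

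Kaplan-Meier estimates for remaining on drug, and cumulative incidence for flare and rescue with discontinuation as the competing event, both censored at the cut-off with numbers at risk, are an acceptable alternative. They are not required: restricting the denominator is enough and is close to what Section 6.6.2 does for binary efficacy.

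The cost is one sentence and a small programming change, with no new data. The downside is that later interim columns will rest on few patients and show lower retention.

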## **7.1 DEMOGRAPHIC AND OTHER BASELINE CHARACTERISTICS**

Only descriptive statistics are planned for this section of the report. Tables will be displayed for SAF-MT, SAF-RT and SAF-FT respectively.

For the continuous variables described below, the following categories will be defined and presented according to the number and percentage of patients in each category:

## **7.2 CONCOMITANT DISEASES AND MEDICATION**

Only descriptive statistics are planned for this section of the report. The analyses of EIM is defined in [Section 7.8.5.2](#).

Analyses of concomitant diseases and medication will be based on SAF-MT, SAF-RT, and SAF-FT, respectively.

Concomitant diseases (i.e., baseline conditions) will be coded according to the most recent version of MedDRA.

Concomitant medication will be coded according to the most recent version of the World Health Organisation – Drug Dictionary.

Concomitant non-drug therapy will be coded according to the most recent version of MedDRA.

### **7.3 TREATMENT COMPLIANCE**

Not applicable since the treatment regimens can be different based on patient status and the version of signed informed consent.

### **7.4 PRIMARY ENDPOINT**

Refer to [section 7.8.1](#) for the description for adverse events including the primary endpoint..

### **7.5 SECONDARY ENDPOINTS**

#### **7.5.1 Key secondary endpoint**

This section is not applicable as no key secondary endpoint has been specified in the protocol.

#### **7.5.2 Secondary endpoints**

*From CTP Section 7.3.2:*

*The evaluation of clinical outcomes based on the MCS, i.e. clinical remission, is based upon the endoscopy results obtained from central reading. Only if the centrally read endoscopy result is missing at a time-point will the locally read result be used instead.*

*For the stool frequency and rectal bleeding items reported in the patient diary, an average of the last 3 non-missing daily assessments collected within the last 7 days prior to the applicable visit will be used for the determination of clinical outcome. If the patient undergoes bowel preparation for endoscopy on any of the days before a visit, the stool frequency and rectal bleeding subscores on that day(s) should be considered to be missing. In addition, the stool frequency and rectal bleeding subscore will be considered to be missing both on the day of and the day after the endoscopy.*

*Secondary endpoint will be assessed descriptively.*

The pre-defined secondary endpoint is described with the corresponding further endpoint in [section 7.6.](#)

## **7.8 SAFETY ANALYSIS**

All safety analyses will be performed based on each of the SAF-MT and SAF-RT following BI standards. No hypothesis testing is planned.

The analyses based on SAF-MT will be done for the pre-flare treatment period (as defined in [Table 6.1: 2](#)), as well as for the overall maintenance treatment period (as defined in [Table 6.1: 4](#)). The analyses based on SAF-FT will be done for the post flare treatment period (as defined in [Table 6.1: 3](#)), as well as for the disease flare treatment period (as defined in [Table 6.1: 5](#)). For additional analysis on the individual flare safety data based on the SAF-FT, all standard

safety tables will be provided for each flare occurrence using the analysis phases as defined in [Table 6.1: 5](#).

In addition, a subgroup analysis on the overall maintenance treatment period by the number of flare treatments (without flare treatment, with only one flare treatment, with two or more flare treatments as defined in [Section 6.4](#)) will be provided for the following tables based on SAF-MT. Additional subgroup analysis (e.g., by pre-flare regimen) will be considered if necessary.

- Overview on TEAE
- TEAE by SOC, preferred term

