5.2.6.2 Adverse event collection and reporting

AE Collection

The investigator shall maintain and keep detailed records of all AEs in the patient files. The following must be collected and documented on the appropriate CRF(s) by the investigator:

- From the time of first dose of trial drug administration in the extension trial until the individual patient's end of trial:
all AEs (serious and non-serious) and all AESIs.
- After the individual patient's end of trial:
the investigator does not need to actively monitor the patient for new AEs but should only report any occurrence of cancer and trial treatment related SAEs and trial treatment related AESIs of which the investigator may become aware of by any means of communication, e.g. phone call. Those AEs should be reported on the BI SAE form (see [Figure 5.2.6.2:1](#)), but not on the CRF.

[figure not shown]

Figure 5.2.6.2: 1 Adverse event collection and reporting

However, patients who discontinue trial medication prematurely and agree to be contacted further should be followed up as described in [section 3.3.4.1](#), withdrawal from trial treatment. From then on until the initially planned completion date of each individual patient the investigator must report all deaths/fatal AEs regardless of relationship, related SAEs and related AESIs the investigator becomes aware of.

AE reporting to sponsor and timelines

The investigator must report SAEs, AESIs, and non-serious AEs which are relevant for the reported SAE or AESI, on the BI SAE form immediately (within 24 hours) to the sponsor's unique entry point (country specific reporting process will be provided in the ISF). The same timeline applies if follow-up information becomes available. In specific occasions the investigator could inform the sponsor upfront via telephone. This does not replace the requirement to complete and send the BI SAE form.

With receipt of any further information to these events, a follow-up SAE form has to be provided. For follow-up information the same rules and timeline apply as for initial information.

Information required

For each AE, the investigator should provide the information requested on the appropriate eCRF pages and the BI SAE form, if applicable.

The following should also be recorded as an (S)AE in the CRF and BI SAE form (if applicable):

- Worsening of the underlying disease or of other pre-existing conditions

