### **Overall Maintenance Treatment Period**

The overall maintenance treatment period applies to all patients taking at least one dose of maintenance treatment regardless of flare occurrence. This period will be considered to understand long-term efficacy and safety of spesolimab.

Table 6.1: 4 Flow chart of analysis phases for overall maintenance treatment period

Study analysis phase	Description	Start (included)	End (included)
Screening  phase	Screening	Earliest of (Date of informed consent, first screening procedure)	Date/time of injection of first maintenance study drug minus 1 minute
Maintenance treatment phase & Residual effects period	Maintenance on-treatment period	Date/time of injection of first maintenance study drug (Day 1 for maintenance)	Date of end of (infusion or injection) of last administered spesolimab + 112 days at 23:59
Follow-up  phase	Off-treatment period	Date of end of (infusion or injection) of last administered spesolimab + 113 days at 12:00 a.m.	Latest of: i) Date of End-of-Study visit; ii) last contact date on End of Study page at 23:59

Dates are defined individually per patient. If more than one date is associated with a specific visit, measurements associated with a specific date are assigned to a study analysis phase according to the rules specified in the table. An analysis phase will not extend beyond the start date of the following phase.

 The off-treatment period (i.e. Follow-up phase) only exists if the trial completion date is after the date of end of last injection or infusion + 112 days.

 The screening phase does not exist for re-induction treated patients who subsequently receive maintenance treatment.

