#### 7.8.1 Adverse events

AEs will be coded with the most recent version of MedDRA.

The analyses of AEs will be descriptive in nature. All analyses of AEs will be based on the number of patients with AEs and not on the number of AEs. System organ classes (if applicable) will be sorted according to the standard sort order specified by the EMA, preferred terms (if applicable) will be sorted by total frequency (within system organ class).

For further details on summarization of AE data, please refer to "Handling and summarization of adverse event data for clinical trial reports and integrated summaries" ([4](#)) [*KM Asset BI-KMED-BDS-HTG-0041*] and "Handling of missing and incomplete AE dates" ([3](#)) [*KM Asset BI-KMED-BDS-HTG-0035*].

The analysis of AEs will be based on the concept of treatment emergent AEs. This means that all AEs will be assigned to the screening phase, re-induction on-treatment period (i.e. re-induction treatment phase plus REP), maintenance on-treatment period (i.e. maintenance treatment phase plus REP) or off-treatment period (i.e. follow-up) as defined in [Section 6.1](#). Adverse events occurring in the maintenance and re-induction periods will be separately described. Since only the start date of an AE is collected (without start time), any AE occurrence on the same day as the first re-induction or first maintenance spesolimab administration will be assigned to the respective on-treatment period. For patients who switch directly to maintenance treatment at week 12 of the re-induction period, adverse events occurring on this first day of maintenance treatment will be included in summaries of the maintenance period only. Exposure-adjusted adverse event incidence rates (per the primary endpoint) will be calculated using the following approach:

- 1) The exposure adjusted incidence rate (per 100 subject years) of a selected treatment emergent adverse event is defined as the number of subjects experiencing the adverse event per treatment group during time at risk divided by the total time of subjects at risk in that treatment group to contribute the event to the analysis multiplied by 100 (per 100 subject years), where:
  - 2) Time at risk [subject years] = (date of onset of AE – study drug start date + 1) / 365.25

For safety analysis on the post-flare treatment periods: Time at risk [subject years] = (date of onset of AE – first i.v. disease flare treatment start date + 1) / 365.25

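### SAP 7.8 splits maintenance-period TEAEs by each patient's eventual number of flare treatments, so the TEAE overview and UC-related rows differ between groups even if flare treatment has no effect

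*SAP*

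**What the plan says.** SAP 7.8 adds "a subgroup analysis on the overall maintenance treatment period by the number of flare treatments", with the categories "without flare treatment, with only one flare treatment, with two or more flare treatments", in SAF-MT. Two tables are named: an overview of TEAEs and "TEAE by SOC, preferred term".

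SAP 6.1 defines the period: "The overall maintenance treatment period applies to all patients taking at least one dose of maintenance treatment regardless of flare occurrence". In Table 6.1: 4 the on-treatment phase opens at the first maintenance injection, before any flare treatment, and closes 112 days after the last spesolimab dose.

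SAP 7.8.1 gives the general clock as "Time at risk [subject years] = (date of onset of AE – study drug start date + 1) / 365.25". A clock that restarts at a flare infusion is defined only for other periods, for example "For safety analysis on the post-flare treatment periods: Time at risk [subject years] = (date of onset of AE – first i.v. disease flare treatment start date". AEs are counted per patient, and both the exposure-adjusted rate and the frequency are tabulated.

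Protocol 5.2.6.2 lists "Worsening of the underlying disease or of other pre-existing conditions" among the items to be recorded as an (S)AE. Protocol 3.1 and Table 2.1:1 define a flare through rises in partial Mayo and rectal bleeding scores, confirmed by endoscopy. No text found exempts flares from AE recording.

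**The concern.** The grouping variable is a post-baseline count. A patient who has a TEAE in month 2 and a flare infusion in month 10 has the early event, and all the early time, placed in the one-flare group. This has two effects.

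- The grouping event is largely also an outcome event. If each flare is recorded as an AE, every patient in the flare groups has at least one TEAE by definition, and the no-flare group has had flares selected out of it while on treatment.
- A patient must stay on drug long enough to reach a flare treatment. Follow-up is therefore longer in the flare groups, which raises their crude frequencies.

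Long-term safety is a main objective, and SAP section 3 says that interim results will support regulatory interactions, Investigator's Brochure updates and publications. A table of TEAEs by number of 1200 mg infusions invites a dose-related reading that its construction cannot support.

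**Working it through.** The documents give no expected subgroup rates, so there is no planned figure to reproduce. The check asks what the tables would show if flare treatment had no effect on any AE.

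**Inputs from the documents**
- Period end: last dose + 112 days, that is 112/365.25 = 0.307 years (SAP Table 6.1: 4).
- Rate: 100 × patients with TEAE / total time to first TEAE or end of period (SAP 7.8.1).
- Flare hazard: the only figure is more than 50% flaring within 6 months among the first 24 responders on the superseded q12w regimen (Protocol 11.4). If constant, this is at least ln 2 / 0.5 = 1.39 per year. Range used: 0.3 to 1.39.

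**Assumptions not in the documents**
- Hazards are constant and the same for everyone: unrelated AEs a = 1.0 per year (0.3 and 2.0 as sensitivity) and other discontinuation d = 0.5 per year.
- A flare is recorded as an AE with probability 1, 0.5 or 0.

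**Closed form, flare hazard f = 0.7, every flare recorded** (ignoring the 336-week cap and the lag from flare to infusion)

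*At least one flare treatment.* Given that flare precedes dropout, the first flare time is exponential with rate f + d = 1.2. The first TEAE is the earlier of that flare and an unrelated AE, so it has rate a + f + d = 2.2. All patients have a TEAE, and the rate is 220 per 100 patient-years.

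*No flare treatment.* Time on drug is also exponential with rate 1.2, but without flares.
- TEAE on drug: 1.0/2.2 = 0.4545. Mean time at risk: 1/2.2 = 0.4545 years. Leaving drug event-free: 0.5455.
- In the 112 days after the last dose the hazard is a + f = 1.7, so the event probability is 1 − exp(−1.7 × 0.307) = 0.406.
- Patients with TEAE: 0.4545 + 0.5455 × 0.406 = 0.676.
- Time at risk: 0.4545 + 0.5455 × 0.406/1.7 = 0.585 years.
- Rate: 100 × 0.676/0.585 = 116.

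The true hazard is 170 per 100 patient-years in everyone. The ratio 220/116 = 1.9 comes from the grouping alone.

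**Simulation of 400,000 patients per scenario** (with the 336-week limit, the 112-day period and a 7-day lag to infusion; a = 1.0)

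| Flare hazard per year | Flares recorded | Any-TEAE rate per 100 PY, 0 / 1 / 2+ | Ratio to no-flare group |
|---|---|---|---|
| 0.3 | all | 105 / 180 / 185 | 1.7 / 1.8 |
| 0.7 | all | 116 / 219 / 221 | 1.9 / 1.9 |
| 1.39 | all | 143 / 287 / 289 | 2.0 / 2.0 |
| 0.7 | half | 108 / 147 / 158 | 1.4 / 1.5 |
| 0.7 | none | 100 / 100 / 100 | 1.0 / 1.0 |

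At f = 0.7 with all flares recorded:
- Any-TEAE frequency is 68% / 100% / 100%.
- The UC term is at 18 / 118 / 121 per 100 patient-years.
- With treatment stopped at the second flare, so that no 2+ group arises, the rates are 118 and 220.

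At f = 0.7 with no flares recorded:
- Crude frequency still differs, 60% / 79% / 88%, because mean follow-up is 1.1 / 2.0 / 2.8 years.
- If 30% of unrelated AEs also stop treatment, rates become 115 / 92 / 89 and the direction reverses.

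The ratio depends on a. At f = 0.7 with all flares recorded, a = 2.0 gives 215 / 320 / 322 (about 1.5), and a = 0.3 gives 48 / 149 / 151 (about 3.1).

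**Check of the remedy.** With events and time split at the first flare infusion and the clock restarted there, any-TEAE rates before and after are 129.7 and 129.9 (f = 0.3), 169.8 and 169.9 (0.7), and 238.6 and 237.8 (1.39). The spurious difference disappears. Under the same constant hazards, a restart at each later infusion gives a + f again in every state.

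**The case against.** The strongest reply is that the time-correct analysis is already planned. SAP 7.8 reports a pre-flare period censored at the first flare infusion, a post-flare period with its own clock, and standard safety tables for each flare occurrence with the clock restarted. SAP 6.1 calls the censored display the primary approach. The two tables are supplementary and descriptive, the protocol already acknowledges bias in this single-arm design, and few patients entered maintenance. This stands and limits the weight of the point. It does not remove it: the two tables would still be produced, no caution on reading them appears in the available text, the post-flare clock does not separate one from two or more treatments, and the per-flare period stops 98 days after the infusion.

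A second reply is that the size is uncertain. Neither document names a flare as an AE, so the effect depends on how sites apply the worsening rule. The flare hazard comes from 24 patients on a superseded regimen. A stress run with withdrawal under the current rule, the 112-day period, and assumed 50% non-response to flare treatment, unconfirmed UC worsening at 0.5 per year and recurrent AEs that stop treatment gave any-TEAE rates of 227 / 338 / 338, a ratio of 1.5. Non-UC frequencies were then 55% / 63% / 62%, so the follow-up gradient nearly vanished while the any-TEAE difference remained.

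SAP 6.4, which 7.8 cites for the categories, is not in the available text, so a caveat there cannot be ruled out.

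Two stronger readings are tempting. A reader might infer that all AE rates are distorted. They are not: for AEs unrelated to flare and to discontinuation, exposure-adjusted rates are equal across groups. A reader might also infer that repeated flare treatment would appear to lower discontinuation for AEs. The documents do not support this. Protocol 3.3.4.1 withdraws patients for flare-related reasons that could themselves be recorded as AE discontinuations, and AEs leading to discontinuation have a separate table that is not one of the two subgroup tables.

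**Conclusion.** The point holds for the TEAE overview and for the UC and gastrointestinal SOC and preferred-term rows of these two tables. Grouping by a later event that is itself recordable as a TEAE makes the groups differ by construction. With no effect of flare treatment, any-TEAE exposure-adjusted rates are roughly 1.4 to 2 times higher in the flare groups. This assumes constant, equal hazards, unrelated AEs at 1 per year, flares at 0.3 to 1.39 per year, and half to all flares recorded. The ratio is larger if unrelated AEs are rarer. The bias can reverse if flares go unrecorded and AEs cause stopping, so a reader could not correct for it by eye. Crude frequencies are affected even when no flare is recorded.

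The primary endpoint is not split by flare count and is unaffected. This is a flaw in two supplementary descriptive tables, worth correcting because the correction is cheap.

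**What to change.** In SAP 7.8, for these two tables only:

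- Replace the eventual count with time-updated status. Assign each TEAE and each day at risk to 0, 1 or 2+ by the flare infusions received up to that day, and restart the first-event clock at each infusion. The dates already define Tables 6.1: 2 to 6.1: 5.
- Base any comparison between groups on exposure-adjusted rates.
- Show those rates with and without preferred terms for worsening of UC.

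The cost is SAP wording and a slightly more complex derivation. No new data are needed.

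Separately, reconcile the category of two or more flare treatments with Protocol 3.3.4.1, which withdraws patients from treatment after more than 1 confirmed flare. Protocol 11.5 shows that this rule replaced an earlier one, so the SAP should state which patients are expected in the category.
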